5.2. Efficacy Assessments

This initial series is designed solely to demonstrate that tumors identifiable under white light will be seen to fluoresce in the near-infrared spectrum after relatively short dwell times. We will document detectability of individual tumors under white light and NIRF at short intervals after Cysview instillation.

5.3. Safety Assessments

Standard patient preoperative assessment will be performed including medical history, physical exam, vital signs, pertinent clinical labs and pre-anesthesia evaluation if deemed necessary. No additional procedures specific to this study will be performed for safety assessment.

5.4. Assessment of Subject Compliance

There are no subject compliance issues to be monitored.

5.5. Costs to the Subject

There will be no cost to the subject. The subject will have no additional research visits. Study medication and the use of the NIRF Imaging equipment will be provided by Imagin Medical.

5.6. Payment for Participation

There will be no payment for participation.

5.7. Return of Individual Research Results

No research results will be provided to the subject. They will have a discussion of resection pathology with their surgeon post procedure as is standard of care.

6. CONCOMITANT AND DISALLOWED MEDICATIONS

No medications will preclude participation. No medications will need to be stopped for participation, except as needed for anesthesia and to undergo TURBT (eg. anticoagulants).

7. SUBJECT WITHDRAWALS

N/A

8. STUDY DRUG/DEVICE/BIOLOGIC ADMINISTRATION/ASSIGNMENT

8.1. Study Drug

Cysview™ (hexaminolevulinate HCL)

[figure not shown]
Study Device

This protocol relies on intravesical administration of an FDA-approved agent for bladder cancer detection (Cysview™) that will fluoresce upon illumination with an FDA-approved cystoscopic light source. This study will use lowered intensities from the light source; near-infrared wavelengths in the spectral region of interest (spectrally overlapping with NIRF signal) that are emitted by a white light source will be removed with a filter to enable detection of the same wavelengths emitted by tumor fluorescence. The imaging system is new.

A standard (FDA-approved) cystoscope that is currently in use in the SMH OR is introduced into the bladder and is used to guide resection of any detected tumors, i.e. Trans Urethral Resection of Bladder Tumors (TURBT). Color and near-infrared image streams will be recorded. The surgeon will be able to display white light images, white light images with pseudocolor highlighting the near-infrared fluorescent tumor, near-infrared image, or any pair of images. Since the NIRF is in a spectrum that is not visible to the human eye, the computer will display this fluorescence in a color that is in the visible spectrum or pseudocolor.

Our imaging system does not fit the definition of significant risk device study and therefore qualifies as a non-significant risk device study as follows:

- NIRF imaging is not an implant and does not present a potential for serious risk to health, safety or welfare of a subject.
- NIRF imaging is not for use supporting or sustaining human life.
- Although NIRF imaging will be used during cystoscopy, resection and pathologic diagnosis of cancer will occur independently to NIRF imaging.
- There is no potential for serious risk to health, safety or welfare of the subject

8.2. Dosage of Study Drug/Biologic

REGIMEN DESCRIPTION					
Agent	Pre-medications; Precautions	Dose	Route	Schedule	Cycle Length
Cysview	None	100 mg	Bladder instillation by catheter	Intraoperative	10 minute maximum

8.3. Subject Enrollment/Randomization

Subjects will be assigned a drug dwell duration based upon the order of study entry. No randomization will occur. The first three study subjects will have a 10 minute dwell time. If the dwell time fluorescence is adequate, dwell time will be reduced to 5 minutes for the next three subjects and then 2.5 minutes accordingly.

8.4. Accountability of Investigational Supplies

Study medication will be stored in a locked cabinet and only accessed by the study team. Study medication will be distributed intra-operatively directly by the study team. Any returned medication will be documented within the study subject's research record and disposed of according to the research pharmacy recommendations. The investigational imaging system will be maintained according to operating room standards. The system will be stored in a locked room and only accessed by the study team.

8.5. **Subject Withdrawal of Study Drug**

Subjects who withdraw from the study will not be eligible to re-enroll in the study.

8.6. **Emergency Drug Disclosure**

As this is not a blinded study, emergency drug disclosure does not apply.

9. SAFETY AND REPORTABLE EVENTS

9.1. **Adverse Event Definition**

An adverse event is any symptom, sign, illness, or experience which develops or worsens during the course of the study, whether or not the event is considered related to the study intervention.

9.2. **Serious Adverse Event Definition**

A serious adverse event is defined as any adverse medical experience that results in any of the following outcomes:

- death
- is life-threatening;
- requires inpatient hospitalization or prolongation of existing hospitalization;
- results in persistent or significant disability/incapacity;
- is a congenital anomaly/birth defect; or
- requires medical or surgical intervention to prevent permanent impairment or damage

9.3. **Recording Adverse Events**

The study staff will assess adverse events by recording all voluntary complaints of the subject post-TURBT (i.e., after Cysview administration in the OR).

All adverse events, whether observed by the Investigator, elicited from or volunteered by the subject, will be documented on the Adverse Event Summary Log. Each adverse event will include a brief description of the experience, the date of onset, the date of resolution, duration, attribution, severity grade, relationship to investigational product (i.e., drug or device), contributing factors, any action taken in response to the study drug/device, and whether the adverse event was expected vs unexpected. The CTCAE (version 4) will be used to assign severity grade of the adverse event.

Adverse events will be documented from the time of Cysview administration until their post-op visit.

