5. METHODS AND STUDY PROCEDURES

The study will be a single center prospective nonrandomized trial of an investigational imaging technology. All patients will undergo investigational imaging and the concomitant standard of care, i.e. transurethral resection of bladder tumor (TURBT). Patients with suspected bladder cancer on cystoscopy will be enrolled to have subsequent intraoperative intravesical administration of Cysview and NIRF cystoscopy prior to TURBT.

Ten patients will be recruited to demonstrate the feasibility of using this NIRF imaging system at shorter intravesical instillation durations (Cysview™ dwell time). The instillation duration will be 10, 5, or 2.5 minutes in this patient series. The subject will be anesthetized, positioned, prepped, and draped for the white light TURBT. A catheter will be passed, Cysview instilled, and the catheter clamped for the assigned dwell time. It will then be unclamped after the dwell time designated, Cysview will be

allowed to drain out, the catheter removed, and cystoscopy performed. The cystoscope is inserted and imaging of the entire bladder commences while recording both color and near-infrared image streams (movies and periodic stills). This initial survey that includes catheterization of the bladder under anesthesia, instillation of Cysview, dwell time as indicated and subsequent evaluation with the color and near-infrared imaging for research purposes. Cysview with blue light cystoscopy has been indicated to be desirable at the time of TURBT but it is not standard of care; it is an optional procedure to increase detection and decrease recurrence. A useful dwell time for Cysview before NIRF imaging will be identified in this study; an effort will be made to minimize the interval between administration and imaging.

The procedure and all study portions will be performed by the subject's surgeon. During the procedure, the bladder will initially be examined in a systematic meridian fashion. Suspicious tumors identified by white light only, NIRF only, and both will be identified. If fluorescence is detected in 3/3 subjects at a given dwell time, the study will continue to shorter dwell times. The initial 3 subjects will have 10 min dwell duration, followed by 5 min and 2.5 min. If fluorescence is not detected in 3/3 subjects at any time period, the study will not progress to shorter dwell times. If no fluorescence is visualized after 10 minutes, we will not proceed to a longer dwell time.

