10.2. Protection Against Risks

To protect subjects from risk, all individuals with hypersensitivity to hexaminolevulinate or any derivative of aminolevulinic acid will be excluded from participation in this study. The installation time utilized in this study will be 10 minutes as compared with the 60 minute instillation time approved by the FDA, further reducing risk of potential adverse events. Subjects will be hemodynamically monitored by anesthesiologists throughout the instillation which will provide early warning of adverse events if any.

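### The adverse event window in section 9.3 opens after the research catheterization, and the section gives two collection rules that do not agree

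*Combined protocol and SAP*

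**What the plan says.** Section 9.1 defines the event broadly: "An adverse event is any symptom, sign, illness, or experience which develops or worsens during the course of the study". The definition includes signs as well as symptoms and does not depend on relationship to the intervention.

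Section 9.3 then says how and when events are collected, in three statements:

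- On method: "The study staff will assess adverse events by recording all voluntary complaints of the subject post-TURBT". A parenthesis equates this with the time after Cysview is given in the operating room.
- On what is logged: "All adverse events, whether observed by the Investigator, elicited from or volunteered by the subject, will be documented on the Adverse Event Summary Log".
- On the window: "Adverse events will be documented from the time of Cysview administration until their post-op visit".

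Section 5 describes the research steps. The subject is anesthetized, a catheter is passed, Cysview is instilled and held for the dwell time, the bladder is drained, and the color and near-infrared survey follows. Resection comes after the survey. Section 5 describes the research component in these words: "This initial survey that includes catheterization of the bladder under anesthesia, instillation of Cysview, dwell time as indicated", followed by the imaging.

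Section 10.2 offers a safeguard for part of this interval: "Subjects will be hemodynamically monitored by anesthesiologists throughout the instillation which will provide early warning of adverse events if any". Section 5.3 adds: "No additional procedures specific to this study will be performed for safety assessment".

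**The concern.** Two things in section 9.3 do not fit the rest of the protocol.

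First, the window begins one step too late. The catheter passed for instillation is a research step by the protocol's own description, yet documentation starts only when the drug goes in. Urethral trauma or bleeding that begins at catheter passage is an adverse event under 9.1 and lies outside the window in 9.3.

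Second, the section tells staff two different things. One sentence has them record what subjects volunteer after resection. The next paragraph has them log what the Investigator sees and what is elicited as well. Staff who follow the first sentence collect less than staff who follow the second.

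The stake is the credibility of a low event count. The interval before resection is the one in which a sign can most easily be told apart from the effects of surgery. Afterwards, hematuria, dysuria, bladder pain and spasm, which section 10.1 lists as known effects of the drug, are also plausible consequences of the resection. Sections 10.2 and 10.3 suggest that the shorter dwell may lower risk. Counts gathered mainly from voluntary reports after surgery would be weak support for that.

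**Working it through.** No figure in the plan bears on this point, so the check sets the procedure sequence in section 5 against the window and sources in 9.3.

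1. **Catheter passage, subject anesthetized.** This is a research step under section 5. It precedes Cysview administration, so it precedes the opening of the window. An event starting here meets the 9.1 definition but is not covered by the 9.3 window.
2. **Instillation and dwell (10, 5 or 2.5 minutes).** These are inside the window. The subject cannot complain, so the voluntary-complaint sentence captures nothing at the time. The second paragraph of 9.3 does apply: a sign observed by the Investigator must be logged. Anesthesiologists are monitoring (10.2), but 9.3 names only the Investigator and the subject as sources and gives no route from the anesthesia findings to the Adverse Event Summary Log.
3. **Drainage and near-infrared survey.** These are inside the window, and the same sources apply. The monitoring statement in 10.2 refers to the instillation and does not mention this step.
4. **Resection, recovery and follow-up to the post-op visit.** These are inside the window. From recovery onward the subject can report, so both rules in 9.3 can work, though one asks for volunteered complaints only and the other also for elicited events.

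Two further comparisons:

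- The parenthesis in the first sentence of 9.3 treats the time after resection and the time after Cysview administration as the same. They differ by steps 2 and 3 and the resection itself.
- The log in 9.3 asks for the date of onset. Research steps and resection fall on the same date, so the date alone cannot place an event before or after the start of resection.

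Result: step 1 is outside the window. Steps 2 and 3 are inside it, with observed events covered but the anesthesia record not named. Across steps 2 to 4 the two collection rules differ.

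**The case against.** The strongest reply is that the anesthetized interval is largely covered. The window opens at drug administration, so dwell, drainage and imaging are in it. The second paragraph of 9.3 requires observed events to be logged, and 9.1 counts signs, so no complaint is needed. Section 5 has the subject's surgeon perform every study step, so a physician is looking into the bladder at the time. Section 9.4 requires all serious events to be documented and notified at once, without any condition that the subject complains. Bleeding caused by the catheter could still be seen at the cystoscopy that follows. Safety is not among the stated aims, and the log already asks for attribution and contributing factors.

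Most of this stands. A reader might infer from the first sentence of 9.3 that voluntary complaints are the only source, or that everything before resection escapes collection, including hypersensitivity signs. The documents do not support either reading: the sentence does not say that it is exclusive, the next paragraph widens the sources, and serious reactions come under 9.4.

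Three things are left unanswered. Seeing catheter bleeding later does not settle whether an event that began before the window should be logged. The anesthesiologist, on whom 10.2 relies, is not a source in 9.3. And the two rules in 9.3 still differ, whichever one staff would follow in practice.

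**Conclusion.** The point holds in a limited form. Section 9.3 as written excludes events that start at the research catheterization, in conflict with the scope of 9.1. It also contains two collection rules that must be reconciled. For dwell and imaging the weakness is narrower: lesser signs noted by anesthesia may not reach the log, because no route is stated.

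The size cannot be given as a number. The excluded interval runs from catheter passage to instillation; it is brief, but it occurs in every subject who receives the study procedure. A reader might try to size the loss from the adverse reaction rate in the appended package insert. That would not measure this gap. The rate counts all reactions after a single instillation, chiefly bladder symptoms, many of which an awake patient would report inside the window. The insert also says that reactions were similar in nature and rate in the study drug and control groups of its controlled study. The documents give no capture rate for voluntary reporting.

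The conclusion assumes that the window statement in 9.3 is applied literally and that no separate working instruction brings the anesthesia record into event collection. It is a modest defect that is worth correcting because the correction is cheap.

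**What to change.** Amend section 9.3 in three places:

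1. Open the adverse event window at passage of the research catheter, not at Cysview administration.
2. Replace the voluntary-complaint sentence with a standard open question to the subject plus events observed by the Investigator, so that it agrees with the paragraph that follows.
3. Name the existing anesthesia and operative records, from catheter passage to the start of resection, as an adverse event source to be reviewed by study staff.

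Optionally, add a field to the log for onset before or after the start of resection, since the date alone cannot show this.

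The cost is protocol wording, a few minutes of record review per subject and slightly more recorded events. No new procedure or staff is needed, and clinical management does not change.

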9.4. Responsibilities for Reporting Serious Adverse Events

All serious adverse events will be documented on the Adverse Event Summary Log and subject's research chart. The principal investigator will be notified immediately of any serious adverse events, and subsequently, the RSRB while complying with regulations and RSRB policy regarding the reporting of adverse events. Since Cysview has a favorable safety profile, we do not anticipate any SAE's in this study.

All serious adverse events will be reported to the Wilmot Cancer Institute's Data Safety Monitoring Committee (DSMC) using the DSMC SAE Review Form. All unexpected and related adverse events will be reported to both the RSRB and to the DSMC within 10 calendar days.

10. RISK/BENEFIT ASSESSMENT

10.1. Potential Risks

Known adverse effects of hexaminolevulinate administration include: headache or procedural pain (1%-10%), bladder spasms (2%), bladder pain, dysuria, hematuria (<10%). Abnormal urinalysis, cystitis have been reported (<1%). Anaphylaxis and hypersensitivity reaction has occurred (<1%). [7]

There is no increased risk of adverse effects from the use of the NIRF imaging system. All medications and equipment components in contact with the subject are FDA approved for use in this patient group. Clinical engineering electrical safety certification will be performed. Cystoscopic light sources approved for human use will be used, but at reduced near infrared intensity for imaging purposes; thus less energy is introduced into the patient than would normally occur.

10.2. Protection Against Risks

To protect subjects from risk, all individuals with hypersensitivity to hexaminolevulinate or any derivative of aminolevulinic acid will be excluded from participation in this study. The installation time utilized in this study will be 10 minutes as compared with the 60 minute instillation time approved by the FDA, further reducing risk of potential adverse events. Subjects will be hemodynamically monitored by anesthesiologists throughout the instillation which will provide early warning of adverse events if any.

10.3. Potential Benefits to Subjects

Blue light cystoscopy with the use of Cysview augments identification of hard to visualize tumors and aids in identifying additional areas requiring tumor resection. The use of Cysview with blue light cystoscopy requires dwell times of 60 minutes that is a logistical challenge. The development of highly sensitive detection equipment may allow a reduction of the Cysview dwell time. The reduction in dwell time may also reduce unintended side effects by reducing the duration of mucosal contact with Cysview.

10.4 Alternatives to Participation

There are no alternatives to participation. This study is voluntary and subjects do not have to participate.

11. CONFIDENTIALITY OF DATA AND INFORMATION STORAGE

All subjects will be assigned a unique code number and the key will be kept on a password-protected database in a locked office of the study team. Signed consent forms, case report forms, and data collection sheets will be kept in binders in the locked office of the Clinical Trials Office.

Imaging data will be kept on a secure Information Systems Division private network server within the University of Rochester Medical Center. This data will be password-protected, accessible only by study team members listed on this study. The data will be kept indefinitely. Only the study team will have access to the data.

12. RESEARCH INFORMATION IN MEDICAL RECORDS

Administration of study medication will be documented in the medical record.

13. DATA ANALYSIS AND MONITORING

13.1. Sample Size Determination

Conventional blue light cystoscopy has a sensitivity of better than 0.9 (90%) for Ta-T4 tumors. Therefore, the probability that we will fail to detect the tumors in three subjects due to the sensitivity of the blue light method is less than 0.001 (0.1%). We thus believe that 3 subjects represent a sufficient sample size to determine the efficacy of this method.

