1. PURPOSE OF THE STUDY AND BACKGROUND

1.1. Purpose of the study

Primary Aim

The primary outcome of this study is to determine the minimal dwell time needed for adequate detection of Cysview avid tumors using protoporphyrin IX (PpIX) near infrared fluorescence (NIRF).

Secondary Aim

To determine in vivo the ratio of intensity of near infrared fluorescence (NIRF) signal arising from the tumor compared to that arising from normal tissue as a function of dwell time.

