2.2. Rationale for Study Design

Although studies have evaluated optimal dwell time for Cysview fluorescence when cystoscopy is performed under blue light, the optimal dwell time for NIRF visualization has not been determined. Prior to conducting randomized studies comparing efficacy of NIRF and blue light we must first establish that a useful and short dwell time can in fact be used successfully. This pilot study will allow us to identify a dwell time for subsequent NIRF cystoscopy studies.

[figure not shown]
Because from a practical point of view, that is the longest time period we want to prolong surgery with a product that should equal or improve on current blue light cystoscopy. We use blue light very selectively now for these reasons: The Dwell study and the subsequent research that comes from it – should permit avoidance of the pre-op catheterization and significantly shorten the procedure. We have found ex-vivo the NIRF imaging is well over 10 times more sensitive to Cysview fluorescence and should have no problem with visualization at 10 minutes.

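### The 0.001 that justifies three subjects per dwell time is the chance of missing all three; the Section 5 rule needs 3 of 3, and the chance of not meeting it is 27% if per-subject detection is 0.90

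*Combined protocol and SAP*

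**What the plan says.** Section 13.1 starts from a blue-light sensitivity above 0.9 for Ta-T4 tumors. It infers that the probability that the study will "fail to detect the tumors in three subjects due to the sensitivity of the blue light method is less than 0.001 (0.1"%), and concludes: "We thus believe that 3 subjects represent a sufficient sample size to determine the efficacy of this method". This is the only numerical basis given for three subjects.

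Section 5 sets the step-down from 10 to 5 to 2.5 minutes:

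- Continue: "If fluorescence is detected in 3/3 subjects at a given dwell time, the study will continue to shorter dwell times".
- Stop: "If fluorescence is not detected in 3/3 subjects at any time period, the study will not progress to shorter dwell times".
- At the first step: "If no fluorescence is visualized after 10 minutes, we will not proceed to a longer dwell time".

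Section 8.3 describes the same three-subject steps with a different trigger: "If the dwell time fluorescence is adequate, dwell time will be reduced to 5 minutes for the next three subjects". It does not mention 3 of 3.

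On purpose, Section 1.1 says: "The primary outcome of this study is to determine the minimal dwell time needed for adequate detection of Cysview avid tumors". Section 2.2 adds: "This pilot study will allow us to identify a dwell time for subsequent NIRF cystoscopy studies".

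**The concern.** The sample size argument and the decision rule concern different events. A figure of 0.001 suggests that a misleading result from three subjects is a one-in-a-thousand matter. Under the continue sentence, though, a single undetected subject is enough to withhold the step to a shorter dwell time, and one miss in three is far more likely than three misses in three.

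What is at stake is the primary outcome. The 3-of-3 rule produces the minimal dwell time that the study will report and carry into later NIRF work. If a cohort falls short by chance at 10 or 5 minutes, a shorter dwell time that works may never be tested, and the result could be read as a true limit of the method. Anyone judging that result from Section 13.1 would think such a chance stop almost impossible. Patient care is not affected, because the resection goes ahead as standard of care whatever the imaging shows.

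**Working it through.** **Inputs**

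- Detection probability p: above 0.90, so 0.90 is the boundary (Section 13.1; a blue-light figure for tumors).
- Subjects per dwell time: 3 (Sections 5 and 8.3).
- Rule to continue: detection in 3 of 3 (Section 5).
- p = 0.95 and p = 0.99: assumptions, used to show the range.
- Subjects are taken as independent.

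**The plan's own figure**

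P(0 of 3 detected) = (1 − p)³. At p = 0.90 this is 0.1³ = 0.001. The stated figure is reproduced, and it is the probability that every one of the three subjects is missed.

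**The probability that belongs to the continue rule**

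P(fewer than 3 of 3 detected) = 1 − p³.

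| p | p³ | 1 − p³ |
|---|---|---|
| 0.90 | 0.7290 | 0.2710 (27%) |
| 0.95 | 0.8574 | 0.1426 (14%) |
| 0.99 | 0.9703 | 0.0297 (3%) |

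Because 1 − p³ falls as p rises, 27.1% is the largest value compatible with p of at least 0.90. To bring 1 − p³ down to 0.001, p would have to be 0.999^(1/3) = 0.9997. If p were below 0.90, the probability would be higher; at p = 0.80 it is 1 − 0.512 = 0.488.

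**The other reading of the stop sentence**

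Suppose that not detected in 3/3 means none of the three. The stop probability at p = 0.90 is then 0.001, which agrees with Section 13.1. The outcomes in between are:

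- 1 of 3: 3 × 0.9 × 0.1² = 0.027
- 2 of 3: 3 × 0.9² × 0.1 = 0.243
- together: 0.270

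These outcomes satisfy neither the continue sentence nor the stop sentence. On this reading the figure fits the stop rule, but 27.0 of the 27.1 percentage points fall where the protocol gives no instruction.

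**What 3 of 3 can show**

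The exact two-sided 95% lower limit for 3 of 3 is 0.025^(1/3) = 0.292, so the interval runs from 29% to 100%. That is compatible with a feasibility aim. It does not determine efficacy.

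**The case against.** The best defence is that Section 13.1 asks a different and sensible question: if all three subjects are negative, could ordinary false negatives of the agent explain it? The answer, about one in a thousand, is right. The sentence in Section 5 on seeing no fluorescence at 10 minutes also concerns complete absence, which lends some support to the 0-of-3 reading of the stop sentence. This stands as a possible reading. It does not rescue the text, because the continue sentence still requires 3 of 3, and 1 of 3 and 2 of 3 are then left open.

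A second objection also stands: p is unknown here. The 0.90 is a blue-light sensitivity for tumors, and the 10% miss rate in the Appendix 2 label is per lesion under blue light, with instillation for about an hour. The Section 5 rule is per subject. Enrolled patients already have a mass seen at office cystoscopy, and Section 5.2 limits the aim to tumors visible under white light, so p could be well above 0.90. The ex-vivo sensitivity gains in Section 1.2 point the same way. Against that, the label says that efficacy is not established for retention under one hour, so p could also be lower.

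A reader might therefore infer too much in three ways:

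- *That this trial has a 27% chance of a false stop.* The documents give no per-subject detection rate for NIRF at any dwell time. The 27% is a value at the plan's own boundary.
- *That there is nearly an even chance of never reaching 2.5 minutes.* Two passes at p = 0.90 give 1 − 0.9⁶ = 46.9%, but this carries the assumption to 5 minutes as well, and nothing in the documents supports that.
- *That Section 8.3 should drop the word adequate.* Adequate detection is the primary aim's own term in Section 1.1, and the data form in Appendix 3 records adequacy. Removing the word would cut that link.

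Finally, this is a pilot without a hypothesis test. Section 5 already speaks of feasibility, and passing at 10 minutes alone would serve much of the purpose in Section 2.2. Stopping after any miss is a defensible, cautious rule. The point is not that the rule or the three subjects are wrong.

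**Conclusion.** The point holds in limited form. The 0.001 is correct arithmetic for all three subjects being missed, but it does not describe the 3-of-3 continue rule. The probability of not meeting that rule is 1 − p³: 27% at 0.90, 14% at 0.95 and 3% at 0.99. Even at 0.99 this is about 30 times the stated figure (0.0297 / 0.001). On the more natural reading of the stop sentence, the justification addresses the wrong event. On the alternative reading, the rule has a gap at 1 of 3 and 2 of 3. The text needs repair either way.

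The sizes rest on independent subjects and on values of p that the documents do not establish for NIRF at 10 minutes or less. The claim in Section 13.1 that three subjects can determine efficacy also goes further than Section 5.2 does. None of this invalidates the data or affects patient care. It matters because the figure is the sole numerical support for the sample size, and the rule generates the primary result.

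**What to change.** Four wording changes:

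1. **Section 13.1, the 0.001 sentence.** Replace with: *A shorter dwell time is tested only if 3 of 3 subjects meet the criterion. The probability that a cohort does not meet this rule is 27% if per-subject detection is 0.90, 14% if 0.95 and 3% if 0.99. The 0.90 comes from blue light cystoscopy and is an assumption for NIRF at 10 minutes or less.*
2. **Section 13.1, the closing sentence.** Replace the claim of sufficiency for efficacy with: *a sample size chosen for feasibility*.
3. **Section 5, the stop sentence.** Replace with: *If fewer than 3 of 3 subjects show fluorescence at a dwell time, no shorter dwell time will be tested.*
4. **Section 8.3.** Refer to the 3-of-3 rule in Section 5 and keep the existing term: *adequate fluorescence in 3 of 3 subjects*.

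Optionally, report the exact 95% interval for detection at each dwell time.

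The cost is protocol text only, with no added patients or procedures. The stated figure becomes less favourable, and 1 of 3 and 2 of 3 become explicit stops. The continue sentence already implies those stops, but the investigators should confirm that they intend them. Three subjects and the 3-of-3 rule are kept, so the change discloses the risk of a chance stop and does not lower it.
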